### **Hypoglycemic events**

At each visit the Investigator will inquire about occurrence of major hypoglycemic events according to the below definition.

Major hypoglycemic event defined as symptomatic events requiring external assistance due to severe impairment in consciousness or behavior, and prompt recovery after glucose or glucagon administration. Plasma glucose measurements may not be available during such an event, but neurological recovery attributable to the restoration of plasma glucose to normal is considered sufficient evidence that the event was induced by a low blood glucose concentration.

Hypoglycemic episodes or symptoms of hypoglycemia will only be reported if the event fulfills the definition of a major hypoglycemic event, the protocol criteria for an SAE or leads to discontinuation of IP.

### **Volume depletion**

Dapagliflozin has a modest diuretic effect. The risk of volume depletion is enhanced when two diuretics are used in combination and in patients that otherwise are at risk for volume depletion. Therefore, caution will be exercised when administering to patients at risk for volume depletion due to co-existing conditions or concomitant medications, such as loop diuretics. These patients will be carefully monitored for volume status, electrolytes, and renal function.

### **UTI**

If the Investigator believes that a UTI may be present, a properly collected set of urine cultures will be obtained and sent to a local laboratory prior to initiation of antibiotic therapy to confirm a presumptive diagnosis of cystitis, urinary tract infection, pyelonephritis. Clinical judgment and local standards of care should apply to decisions concerning therapy.

In patients with clinical evidence of upper UTI (e.g., pyelonephritis) or presumed urosepsis, the Investigator may consider temporarily stopping IP until the course of treatment of the infection has been completed and clinical recovery has occurred. It is recommended that a follow-up urine culture is obtained within 7 days of clinical recovery from a documented UTI.

### **Asymptomatic bacteriuria**

During enrollment, randomized treatment and follow up of patients in this trial, the Investigator may discover a patient with asymptomatic bacteriuria. Asymptomatic bacteriuria is defined as the presence of  $\geq 10^5$  colony forming units/mL of bacteria, in a properly collected voided urine specimen, without signs or symptoms typically attributed to urinary tract infection. Asymptomatic bacteriuria is prevalent among diabetic women, and is associated with pyuria in 70% of cases.

### **Adjudication of suspected CV endpoints**

The primary outcome of the study is to compare the efficacy of dapagliflozin compared with placebo, on the composite rate of hospital admissions, emergency department visits, urgent clinic visits for HF and death after admission with ADHF.

Definition of heart failure hospitalization, emergency department visit and urgent ambulatory heart

failure is included in Appendix A.

Suspected CV outcome events in the study will be identified either by the Investigator and reported AEs. For all events identified for adjudication the Investigator will enter information in the eCRF and provide source documentation.

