**Innovation.** The proposed study will be the first prospective RCT to determine the safety and efficacy of dapagliflozin treatment in preventing readmissions/ER visits/urgent clinic visits and death in patients with and without T2D after admission for ADHF. Treatment with SGLT2-i has been shown to reduce both HF hospitalization and mortality in patients with established heart disease and a history of HF . More recently, among patients with HFrEF, dapagliflozin was shown to reduce the risk of worsening heart failure or death from cardiovascular causes compared to placebo, regardless of the presence or absence of diabetes . However, the time of initiation of SGLT2-i therapy has yet to be formally evaluated in patients with ADHF and is the purpose of this study. In addition, we will evaluate the impact of treatment on HF symptoms quality of life, resource utilization and cost-effectiveness of dapagliflozin versus placebo. The results of this study have great potential to influence and facilitate care and to change current clinical guidelines in the management of patients with ADHF.

**Rationale on Dapagliflozin treatment.** Dapagliflozin (Farxiga®) is a highly selective SGLT2-i, given in once-daily doses. It is rapidly absorbed with a time to maximum plasma concentration of two hours and a half-life of 17 hours, with an absolute oral bioavailability of dapagliflozin following the administration of a 10 mg dose of 78%. Dapagliflozin is approximately 91% protein bound. Protein binding is not altered in patients with renal or hepatic impairment. The metabolism of dapagliflozin is primarily mediated by UGT1A9; CYP-mediated metabolism is a minor clearance pathway in humans. Dapagliflozin and related metabolites are mainly eliminated via the renal pathway. The mean plasma terminal half-life for dapagliflozin is approximately 12.9 hours following an oral dose of Farxiga 10 mg.

Clinical trial in ambulatory patients with T2D reported a significant reduction in HbA1c of ~ 0.8%-1.5% from baseline in patients with T2D. Dapagliflozin as monotherapy and in combination with other antidiabetic drugs is well tolerated and associated with very low rates of hypoglycemia. In addition, due to its mechanism of action of increasing urinary glucose excretion, SGLT2-i can reduce systolic blood pressure and body weight compared to placebo in patients with T2D.

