SGLT2-is have been shown to markedly reduced HF hospital admissions in patients with and without diabetes. In the CVD-Real Study, which included 961 HF cases, SGLT2-i reduced the rates of HF hospitalizations hazard ratio, 0.61; 95% confidence interval, 0.51-0.73; P<0.001. The CVD-Real 2 multinational study of 235,064 patients with T2D, initiation of an SGLT-2i was also associated with a lower risk of all-cause death and hospitalization for heart failure, as compared to other glucose lowering drugs. The use of SGLT-2i vs. other glucose lowering drugs was associated with lower risk of death and heart failure. Recent RCT examining cardiovascular outcome using SGLT2-i reported a significant reduction in hospitalization for HF. In the DECLARE trial, dapagliflozin resulted in lower rate of hospitalization for heart failure compared to placebo (HR, 0.73; 95% CI, 0.61 to 0.88). The EMPA-REG OUTCOME study showed a 35% reduction in HF hospitalizations. In addition, in the CANVAS Program the benefits were greater in patients with a previous history of HF compared with those without HF at baseline (HR, 0.87; 95% CI, 0.72–1.06; P interaction = 0.021). In the Canvas Program, the rate of HF was reduced in patients with history of HF from 28.1% to 14.1% between patients treated with canagliflozin and placebo.

Based on data summarized above, we assume the composite event rate in the placebo group is between 40-60%, which would be reduced by 30% in the dapagliflozin group. Based on two-sided Chi-square test, with preserved alpha=0.05, with 176 subjects, we would achieve over 80% power to detect a 30% reduction in proportion of patients with readmission, ER visits, urgent unplanned clinic visit for HF or death if the composite event rate in the placebo group is 50%. Accounting for 10% attrition, we propose to recruit 392 patients (196 per group).

In the table below, we provide estimated power based on the same method, corresponding to different placebo composite event rates that are between 40-60%:

Composite event rate in the placebo group	40%	45%	50%	55%	60%
Estimated Power	62%	72%	82%	88%	93%

The results in the above table suggest promising power for the proposed study.

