We will implement an adaptive design with conditional power calculation and potential for re-estimation of the sample size, if necessary, after the interim analysis scheduled to be performed after 50% of the patients were enrolled and completed the 26 weeks of study period (196 patients) and undergone adjudication of the primary composite endpoint. Sample size re-estimation will be performed based on the observed composite event rate per group at the time of the interim analysis. See below “interim efficacy analysis”.

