- Suspected transmission of an infectious agent (e.g. pathogenic or nonpathogenic) via the study drug is an SAE.

**NOTE:** The following hospitalizations are not considered SAEs:

- a visit to the emergency room or other hospital department < 24 hours, that does not result in admission (unless considered an important medical or life-threatening event)
- elective surgery, planned prior to signing consent
- admissions as per protocol for a planned medical/surgical procedure
- routine health assessment requiring admission for baseline/trending of health status
- medical/surgical admission other than to remedy ill health and planned prior to entry into the study.
- admission encountered for another life circumstance that carries no bearing on health status and requires no medical/surgical intervention (e.g., lack of housing, economic inadequacy, caregiver respite, family circumstances, administrative reason).

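### Entry to adjudication relies on the investigator and AE reports, which is weak for ED and urgent clinic visits, and the encounter data already planned for costs are not reconciled with the primary endpoint

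*Combined protocol and SAP*

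**What the plan says.** The section Adjudication of suspected CV endpoints gives the only case-finding rule for the primary composite: "Suspected CV outcome events in the study will be identified either by the Investigator and reported AEs". It adds: "For all events identified for adjudication the Investigator will enter information in the eCRF and provide source documentation". It describes no screen of all encounters, no list of objective triggers, and no masking of the adjudicators.

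What the AE route can deliver is set in Definition of Adverse Events. Inpatient admission and death are SAEs, and Reporting of serious adverse events requires all SAEs to be reported whatever their cause. A listed exception to SAE status is "a visit to the emergency room or other hospital department < 24 hours, that does not result in admission", unless the event is medically important or life-threatening. An urgent clinic visit is not an SAE criterion. AEs are gathered from spontaneous report, open-ended questioning or examination, and staff are told not to ask about specific AEs.

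The same encounters are collected a second time. Aim 3 plans prospective collection of ER visits, urgent clinic visits for HF and hospitalizations. Item 12 of Measurements During follow-up takes cost data from electronic medical records. Cost-Effectiveness Analyses makes the numbers and incidences of these visits endpoints. No section links these data to the primary-endpoint file.

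**The concern.** Adjudication can reject a referred event, but it cannot add one that was never referred. The composite counts ED visits and urgent clinic visits for HF alongside admissions and death, and these are the components on which the referral route is thinnest. A patient treated and sent home from an ED enters only if the patient mentions it or the site notices it, and the site then records it. The Schedule of Assessments has an AE row at every contact but no row for healthcare encounters.

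Two consequences are possible. If visits are missed equally in both arms, the event rate falls and so does power. If they are missed more often in one arm, the comparison is biased. The interim analysis is exposed as well: it is timed on patients who have "undergone adjudication of the primary composite endpoint", and sample size is re-estimated from the event rate observed per group, so under-capture would feed into that decision.

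**Working it through.** **Inputs from Statistical Methods.** "Based on two-sided Chi-square test, with preserved alpha=0.05, with 176 subjects", and "we would achieve over 80% power to detect a 30% reduction in proportion of patients" when the placebo rate is 50%, so 50% vs 35%. Attrition is 10% and 196 per group are recruited.

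**The plan's own figure.** With d = p1 − p2 and p̄ = (p1 + p2)/2:

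- se0 = √[2p̄(1 − p̄)/n]
- se1 = √[(p1(1 − p1) + p2(1 − p2))/n]
- power = Φ[(d − 1.96·se0)/se1]

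At n = 176 per group, 0.50 vs 0.35:

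- se0 = √(2 × 0.425 × 0.575/176) = 0.0527
- se1 = √((0.25 + 0.2275)/176) = 0.0521
- power = Φ[(0.15 − 0.1033)/0.0521] = Φ(0.897) = 81.5%

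This matches the stated 82%. The 176 must be per group, since 88 per group gives 52%; and 176/0.9 = 195.6, which rounds up to 196. The formula does not match the table's 40% and 45% columns (66.3% and 74.3% against the stated 62% and 72%), but that does not bear on this point.

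**Assumptions (not in the documents).** Let s be the share of event patients who qualify only through an ED or urgent visit, and m the fraction of those missed. Both range from 10% to 30%. Analysis of Primary Endpoint counts patients with at least one event, so a missed visit matters only if it was the patient's sole qualifying event. The observed rate is therefore p × (1 − s·m).

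**(a) Equal misses, true 50% vs 35%.** The risk ratio stays at 0.70.

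| s, m | Observed rates | Power |
|---|---|---|
| 10%, 10% | 49.5% vs 34.65% | 80.8% |
| 20%, 20% | 48.0% vs 33.6% | 78.7% |
| 30%, 30% | 45.5% vs 31.85% | 75% |

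**(b) No true effect, misses on dapagliflozin only.** Type I error adds both tails: Φ[(d − 1.96·se0)/se1] + Φ[(−d − 1.96·se0)/se1]. At a 50% rate with s = m = 30%, the observed rates are 50% vs 45.5%, so d = 0.045 and se0 ≈ se1 ≈ 0.0532. The tails are Φ(−1.116) = 0.132 and Φ(−2.808) = 0.0025, together 13.5%.

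| True rate, both arms | s = m = 10% | s = m = 20% | s = m = 30% |
|---|---|---|---|
| 40% | 5.1% | 6.1% | 10.7% |
| 50% | 5.1% | 6.6% | 13.5% |
| 60% | 5.2% | 7.4% | 17.6% |

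**(c) True 50% vs 35%, misses on dapagliflozin only.** With s and m between 20% and 30%, the apparent risk ratio is 0.67 to 0.64 instead of 0.70.

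**The case against.** The best defence is that the plan has more safeguards than the adjudication section suggests, and much of this stands.

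- Admissions and deaths are SAEs, all of which must be reported. Vital status is sought even after withdrawal.
- Worsening HF meets the AE definition, and identified non-serious AEs are recorded. A short ED visit is therefore not shut out merely because it is not an SAE.
- Measurements During follow-up lists the components of the composite, each AE carries a flag for a potential endpoint, and patients who refuse visits are still followed for endpoints.
- The bar on asking about specific AEs does not bar asking about visits.

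These limit the gap but do not close it. The flag exists only once the site has recorded an AE, the endpoint contacts under modified follow-up serve only patients who decline visits, and vital-status checks recover deaths only.

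A reader might infer four stronger things that the documents do not support.

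1. *Missed events are unrecoverable.* The record abstraction for costs could recover many. What is missing is the rule that uses it.
2. *Urine results unblind the investigator.* The rationale notes that SGLT2 inhibitors act "due to its mechanism of action of increasing urinary glucose excretion", and no masking rule for urine results is stated. But no post-randomization urine glucose is ordered. The named tests are sodium, albumin/creatinine ratio, ketones, a pregnancy test, hematuria microscopy and culture ("a properly collected set of urine cultures will be obtained and sent to a local laboratory"). Unblinding through an incidental result is conceivable but not documented.
3. *Mislabelled admissions are lost endpoints.* Appendix A requires a primary diagnosis of HF, so an admission with another primary diagnosis is not an endpoint.
4. *Power falls to 74% or 66%.* Those figures require 10% or 20% of all event patients to be missed, including deaths and admissions, which are the well-protected components.

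The Event Reporting Manual cited for liver events and malignancies may hold more detail. It is not among the documents, and the CV adjudication section does not cite it.

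**Conclusion.** The point holds in a limited form. The plan states a case-finding rule that depends on the site and is weak for ED visits under 24 hours and urgent clinic visits, and it leaves a second record of the same encounters unused for the primary endpoint. Under the assumed 10-30% ranges, the likely cost is modest: power of 81% to 75% instead of 81.5%. A false-positive bias (type I error of 5.1-13.5% at a 50% rate) arises only if referral differs by arm, and the documents give no evidence that it would. The shares and miss rates are assumptions throughout. This should be repaired because the remedy uses data already planned, not because bias has been shown.

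**What to change.** In Adjudication of suspected CV endpoints and the Schedule of Assessments:

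1. At each of the 8 post-discharge contacts (5 clinic, 3 phone), ask a fixed question about any hospital stay, ED visit or unscheduled clinic visit since the last contact.
2. Before the interim and final locks, reconcile the answers and the record abstraction planned for costs with the endpoint file.
3. Send every death, and every encounter with a primary diagnosis of HF or intensified HF treatment, to adjudicators masked to treatment for review under Appendix A, whether or not the investigator suspects an endpoint. State the masking.
4. At most, add that any incidental post-randomization urine glucose result is neither used in nor passed on with endpoint referral. No limit on urine testing is needed; the UTI and Hematuria sections leave that work-up to clinical judgment and local standards.

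The cost is protocol wording, one item on the contact form, more record requests and more adjudication packets, some of which will not qualify. Record abstraction must also be current by the interim lock.

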### **Reporting of serious adverse events**

Investigators and other study site personnel will inform the Emory IRB, FDA and sponsor (AZ) of any SAE via a MedWatch/AdEERs form that occurs in the course of the study immediately or within 24 hours of when he or she becomes aware of it. Follow-up information on SAEs will also be reported by the Investigator with the same time frame. It is the responsibility of the investigator to compile all necessary information and ensure that the Emory IRB, sponsor and FDA receives a report according to the FDA reporting requirement timelines and to ensure that these reports are also submitted to AstraZeneca at the same time.

All SAEs have to be reported, whether or not considered causally related to the investigational product, or to the study procedure(s). All SAEs will be recorded. All SAEs collected in the study are to be reported to AstraZeneca.

The causality of SAEs (their relationship to all study treatments/procedures) will be assessed by the investigator(s) and communicated to AstraZeneca.

The Investigator is responsible for informing the local authorities and ethical committees, of any SAEs as per local requirements, and concurrently AstraZeneca.

SAEs that do not require expedited reporting need to be reported to AstraZeneca at least quarterly, preferably as they occur, either as individual case reports or as line listings.

When reporting to AstraZeneca, a cover page should accompany the SAE form indicating the following:

- External Sponsored Research (ESR)
- The investigator's name and address
- The trial name/title and AstraZeneca ESR reference number

Investigative site must indicate, either in the SAE report or the cover page, the causality of events in relation to all study medications.

Send SAE report and accompanying cover page by way of fax to AstraZeneca's designated fax line: [contact] or email if a secure is set up: [[contact]](mailto:[contact])

### **Hypoglycemia risk protection:**

We will follow safeguards to minimize the risk to our subjects: a) we will carefully monitor response to medical treatment every 2 weeks by telephone contact and during clinic visits, b) women of reproductive age who are sexually active will undergo a urine pregnancy tests prior to participation in the study, c) patients with significant comorbidities such as chronic kidney disease greater than stage II, cirrhosis, gastroparesis, and pancreatic disease will be excluded from the study.

**Hypoglycemia:** We expect that less than 10% of dapagliflozin treated patients will experience hypoglycemia during follow-up; however, approximately 20% to 30% of subjects treated with basal insulin and study drug will experience one or more episodes of hypoglycemia. Patients will receive diabetes education prior to discharge and will be instructed on hypoglycemia sign/symptoms and

treatment. Patients will be asked to call the T2D center and/or PCP in the event of hypoglycemia. If a patient develops hypoglycemia, the daily dose of insulin will be reduced by 10% to 30%.

### **Treatment of Hypoglycemia (BG <70 mg/dL)**

For BG < 70 mg/dL, follow hypoglycemic orders below:

- If patient is alert and can tolerate oral intake, give 20 grams of fast-acting carbohydrate (6 oz. fruit juice or regular soda, crackers).
- If patient is not alert and cannot tolerate oral intake, call 911, give 1 mg glucagon IM or SQ
- Check finger stick BG q 15 minutes and repeat above treatment until BG > 100 mg/dL.
- Once BG > 100 mg/dL, repeat finger stick BG 1 hour later and provide a meal or carbohydrate

**Potential Benefits to the Subject:** We believe that all subjects will benefit greatly from this study.

Improved glycemic control after hospital discharge may significantly reduce complications and reduce readmissions as well as the risk of hyperglycemia and hypoglycemia.

**Potential Benefits to Society:** This study will provide important information on the benefits of dapagliflozin after discharge for the management of patients with T2D. We will determine whether glycemic control is different among insulin and dapagliflozin after hospital discharge.

**Risk/Benefit Assessment:** There are no prospective, randomized studies to assess the efficacy and safety of dapagliflozin for the management of T2D after hospital discharge in patients with a recent HF admission. This study will test the efficacy of dapagliflozin in preventing hospital readmissions during the following 6-months after hospital discharge in patients with and without diabetes.

**Therapeutic Alternatives:** Patients can be treated with insulin regimen and oral agents (glyburide, glipizide, DPP4 inhibitors and GLP1 analogs) currently available for the treatment of T2D. In addition, there are several well-established medications that have been proven effective in improving cardiac function in patients with a history of heart failure.

**Inclusion of women.** We anticipate that ~50% of the study subjects will be female. No patients under the age of 18 and no pregnant women will be included in the study. Absence of pregnancy will be demonstrated by blood or urine testing prior to randomization (in female of childbearing potential only).

**Inclusion of minorities.** Patients will not be excluded based on race or ethnic origin. We anticipate that half of patients will be African Americans, 10% Hispanics, and the rest Caucasians.

**Inclusion of children.** No patients under the age of 18 will be recruited in this study.

**Confidentiality.** Informed consent will follow the procedure of Emory University Institutional Review Board. Every potential participant will be informed in writing and verbally with the important and key points of the study. The research team will obtain a witnessed informed consent prior to inclusion of a patient into the study. Data collection records with personal identifiers will be stored in locked file cabinets. Presentation of the study results at scientific meetings or in publications will not identify subjects. Access to research and confidential records will be limited to clinical investigators, coordinators and the IRB at Emory University.

**Payment for Participation.** Participation in this study is voluntary. Patients will receive twenty-five dollars (\$25.00) during the hospital stay and visit 2, and fifty dollars (\$50.00) after each clinic visit after discharge. Total compensation up to three hundred dollars (\$300).

**Financial Obligation.** No additional cost to patients or to the institution will be incurred for research purposes. Research studies will be performed at no cost to study subjects. Dapagliflozin and matching placebo will be provided by the sponsor at no cost to participants.

**Research Injuries.** If a patient is injured because of taking part in this study, [name] and investigators, along with the medical facility will make medical care available to the patient at the patient's own cost. Financial compensation for such things as lost wages, disability or discomfort due to an injury related to the study is not available.

**Financial Conflict of Interests.** None of the investigators in this study have any outside activities that may represent a conflict of interest. None of the investigators have an economic interest in an outside entity, or act as officers, directors, employees or consultants with such an entity, whose financial interest may be affected by this research study.

**Informed Consent.** After identification of eligible patients these individuals will be provided basic information regarding the study and, if interested, they will then be screened by research staff using the inclusion/exclusion criteria delineated elsewhere in this protocol. The consent form, potential risks and benefits, and the rights of research participants will be explained to the participant by the investigators or research coordinator. Individuals will be asked if they have any questions, and research staff will answer these questions. The principal investigator will also be available to answer questions that participants may have during the consent procedure or during the time a participant is enrolled in the study. The consent form will be completed in accordance with the IRB guidelines of Emory University. A signed copy of the consent form will be provided to the participant and a copy will be placed in the file that is maintained for each participant in the study office.

